10.4. IMMUNOGENICITY

Serum samples will be collected prior to dose at Day 1, Weeks 3, 9, 24, 36 and 48 (or PW). If a subject tests positive for ADA after confirmatory and reactive titer testing, the sample will then be tested for neutralizing antibody (NAb). If the subject tests positive for NAb, he/she will be followed until levels either revert to Study Baseline or the subject's value decreases or remains stable.

Immunogenicity endpoints include:

- Incidence of ADA and NAb (out of positive ADA samples, if applicable) by visit and provided by treatment received in HZNP-TEP-301

The count and percent of subjects will also be provided by treatment received in HZNP-TEP-301 for the following:

- Overall positive ADA result, defined as at least one confirmed positive antibody
- Cumulative negative ADA result, defined as negative ADA results at all time points for a subject
- A negative ADA on HZNP-TEP-302 Day 1 and a positive result at any post-dose visit

Immunogenicity sampling times and results will be listed.

Further, the mean and CV% (calculated as $100\% \times SD/mean$) of pre-dose serum concentrations will be provided by visit in the subset of subjects who are confirmed ADA positive, NAb positive (if applicable) and ADA negative for each visit. This analysis will be provided for the PK Population.

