#### 9.5.4.7 Immunogenicity Testing

Blood samples will be collected in a 5 mL SST collection tube for immunogenicity testing (ADA and possibly Neutralizing Antibodies [NAb]) from all subjects prior to dosing on Day 1, prior to dosing on Weeks 3 and 9, and at Week 24 of the Treatment Period, and Months 9 and 12 (or PW) of the Follow-Up Period. Samples will be collected, processed, and stored at  $\geq -70^{\circ}\text{C}$  at the site until shipment to the central laboratory [REDACTED] will store the samples at  $\geq -70^{\circ}\text{C}$  until shipment to [REDACTED] for immunogenicity testing. If a subject tests positive for ADA after confirmatory and reactive titer testing, the sample will then be tested for NAb. If the subject tests positive for NAb, he/she will be followed until levels either revert to Baseline or the subject's value decreases or remains stable. Any subject with a positive NAb test

at Month 12 (or PW) of the Follow-Up Period will continue to be followed until the subject's value decreases or remains stable.

Instructions for processing, handling, storing, and shipping of immunogenicity samples will be detailed in a laboratory manual that will be provided to each site prior to site initiation.

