After completion of the Treatment Period, subjects who were proptosis non-responders in Study HZNP-TEP-301 will enter a 24-week Follow-Up Period, during which study drug will not be administered and clinic visits are scheduled for 1, 3, and 6 months (Visits Month 7, 9 and 12) after the Week 24 visit; if any of these subjects discontinue from the Follow-Up Period prior to the Month 12 Visit, they will return to the clinic and undergo the scheduled Month 12 assessments prior to study discharge. Those who complete the Month 12 visit will be contacted at 6 and 12 months later via phone or email by research staff to enquire if any treatment for TED has been received since last study contact. If yes, subject will be questioned regarding type of treatment and outcome/response.

Subjects who relapse during the Follow-Up Period of HZNP-TEP-301 and choose to enter this extension study will not participate in the Follow-Up Period. For these subjects, the last clinic visit is at Week 24. Those who complete the Week 24 visit will be contacted 6 and 12 months later via phone or email by research staff to enquire if any treatment for TED has been received since last study contact. If yes, subject will be questioned regarding type of treatment and outcome/response.

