PK samples ²³	X	X	X	X		X					X ²¹							
Contact (phone/email) to assess additional TED treatment ²⁴															X	X	X	X

ADA=anti-drug antibody; AE=adverse event; CAS=Clinical Activity Score; ECG=electrocardiogram; FT3=free triiodothyronine; FT4=free thyroxine; FU=Follow-Up; GO-QoL=Graves' Ophthalmopathy Quality of Life Questionnaire; HbA1c=glycated hemoglobin; M=month; NAb=neutralizing antibody; PK=pharmacokinetic; PW=premature withdrawal; SAE=serious adverse event; TED=thyroid eye disease; TSH=thyroid stimulating hormone; W=week.

Footnotes:

1. Open-label Treatment Period. Subjects with TED who are proptosis non-responders at Week 24 of HZNP-TEP-301 or were proptosis responders at Week 24 but who meet criteria for re-treatment due to relapse during the Follow-Up Period in HZNP-TEP-301 are eligible to enroll and receive 8 infusions of teprotumumab (10 mg/kg for the first infusion titrated to 20 mg/kg for the remaining infusions) in an open-label fashion.
2. Proptosis non-responders from Study HZNP-TEP-301 will participate in a 6-month Follow-Up Period; subjects who relapsed during the Follow-Up Period of HZNP-TEP-301 will not participate.
3. Proptosis non-responders from Study HZNP-TEP-301 who complete the Month 12 Visit and subjects who relapsed during the Follow-Up Period of HZNP-TEP-301 and complete the Week 24 Visit will be contacted via phone or email by research staff to enquire if any treatment for TED has been received since last study contact.
4. If subjects wish to discontinue study drug during the open-label Treatment Period, subjects will return for a clinic visit and undergo the Week 24 assessments, except for PK and ADA evaluations. Subjects who were proptosis non-responders at Week 24 of HZNP-TEP-301 will be encouraged to continue study participation in the Follow-Up Period.
5. If a subject wishes to prematurely discontinue from the study during the Follow-Up Period, he/she will return for a clinic visit and undergo the Month 12 assessments prior to discharge.
6. On Day 1 (Baseline), subjects will receive the first dose of study drug; however, Baseline assessments will be performed prior to dosing.
7. Day 1 will occur within 14 days after the final visit of Study HZNP-TEP-301 (Week 24 for proptosis non-responders and up to Week 72 for subjects who relapse).

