15. Vital signs (heart rate, blood pressure, respiratory rate, temperature) will be measured at all clinic visits. Vital signs will be measured pre- and post-infusion on Day 1 and Week 3, and pre-dose on all other infusion days. Additional vital signs will be monitored if infusion-associated AEs occur.
16. Non-diabetic subjects should be fasting at Weeks 1 and 4 only. Diabetic subjects should be fasting at each visit blood glucose is evaluated.
17. ALT/AST must be ≤ 3 x the upper limit of normal (ULN) and serum creatinine must be < 1.5 x the ULN (according to age) at the most recent clinic visit to be eligible for enrollment.
18. Subjects must be euthyroid with the baseline disease under control or have mild hypo- or hyperthyroidism (defined as free thyroxine [FT4] and free triiodothyronine [FT3] levels $< 50\%$ above or below the normal limits) at the most recent clinic visit. Every effort should be made to correct the mild hypo- or hyperthyroidism promptly and to maintain the euthyroid state for the full duration of the clinical trial.
19. HbA1c must be $< 9.0\%$ at the most recent clinic visit. If the HbA1c is elevated and considered clinically significant at any time point after Baseline, it will be repeated approximately every 45 days until it returns to normal or the baseline value.
20. If a sample is positive in the ADA test, after confirmatory and reactive titer testing, the sample will then be tested for NAb. If the subject tests positive for NAb, he/she will be followed until levels either revert to Baseline or the subject's value decreases or remains stable. Any subject with a positive NAb test at Week 48 (or PW) during the Follow-Up Period will continue to be followed until the subject's value decreases or remains stable.
21. Not collected for subjects who prematurely discontinue from the open-label Treatment Period.
22. Adverse events that are ongoing at completion of HZNP-TEP-301 and/or occur prior to dosing on Day 1 will be considered pre-dose AEs. Adverse events occurring or worsening after the dose on Day 1 through the end of the Treatment Period will be considered treatment-emergent AEs (TEAEs). Adverse events occurring or worsening during the Follow-Up Period will be considered postdose AEs. All SAEs that occur from the signing of informed consent through 30 days after study discontinuation will be recorded.

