6.2.3. Study Baseline and HZN-001 Baseline

The following two definitions of baseline will be utilized for analysis purposes:

- **Study Baseline** will be defined as the last measurement taken prior to first dose in HZNP-TEP-302 (considering unscheduled visits when available). If a Study Baseline value is not obtained in the HZNP-TEP-302 study prior to dosing, the last value measured in HZNP-TEP-301 will be used. Study Baseline comparisons will be provided for all applicable endpoints.
- **HZN-001 Baseline** will be defined as the last measurement taken prior to first dose of HZN-001 whether it occurred in HZNP-TEP-301 or HZNP-TEP-302 (considering unscheduled visits when available). HZN-001 Baseline comparisons will be provided for select assessments of safety, i.e. laboratory assessments, vital signs, ECGs, physical examinations, and ophthalmic examinations.

Change from (Study or HZN-001) Baseline will be defined as the measurement at each time point minus the relevant Baseline value.

The primary objective will be assessed using the Study Baseline.

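### SAP 10.4's subject-level ADA measures pool subjects with 3 and 5 post-dose samples, and the measure of new positivity keeps Day 1 positives in its denominator with no summary of titer rise on re-treatment

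*SAP*

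**What the plan says.** ADA is sampled before dosing on Day 1 and at Weeks 3, 9 and 24, "and Months 9 and 12 (or PW) of the Follow-Up Period" (Protocol 9.5.4.7). The last two visits exist only for lead-in proptosis non-responders: "Subjects who relapse during the Follow-Up Period of HZNP-TEP-301 and choose to enter this extension study will not participate in the Follow-Up Period" (SAP 3.4). For the Week 24 sample, a footnote to the SAP 3.8 schedule adds: "Not collected for subjects who prematurely discontinue from the open-label Treatment Period".

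SAP 10.4 plans ADA incidence by visit and three subject-level measures, all by lead-in treatment:

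- "Overall positive ADA result, defined as at least one confirmed positive antibody"
- cumulative negative, meaning negative at every time point
- "A negative ADA on HZNP-TEP-302 Day 1 and a positive result at any post-dose visit"

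Section 10.4 states no denominator for these three. The default in SAP 14.2.5.2 is every subject in the column with an observation. The table index (SAP 16) lists one ADA incidence table, Table 14.3.4.4.3, and no version by enrollment type.

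On baselines, SAP 6.2.3 says "HZN-001 Baseline comparisons will be provided for select assessments of safety" and then names laboratory tests, vital signs, ECGs, and physical and ophthalmic examinations. Immunogenicity is not among them.

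**The concern.** There are two separate problems.

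**Unequal sampling.** All three subject-level measures accumulate over visits. More samples give more chances to be ever positive and fewer chances to be always negative. The number of samples depends on enrollment type, but the measures are split only by lead-in treatment, so each column can mix both schedules. The SAP avoids this elsewhere. Section 10.3 reports follow-up adverse events separately, over the subjects who entered follow-up, and sections 10.1 and 10.2 split exposure and compliance by enrollment type.

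**Reference point after earlier exposure.** In the HZN-001 column, HZNP-TEP-302 Day 1 comes after the lead-in teprotumumab course. A subject who is already ADA-positive that day cannot meet the third measure, whatever re-treatment then does to the titer, but remains in its base. Titer testing is part of the assay sequence in SAP 10.4, yet no titer change is summarized. The tables therefore cannot show whether a second course raises an existing antibody response.

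**Working it through.** The documents give no ADA rate, no relapse count by lead-in arm and no sample size calculation, so there is no planned figure to reproduce. The probabilities and shares below are assumptions.

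**Step 1. Post-dose samples (Protocol 9.5.4.7; SAP 3.4 and 3.8).**
- Relapse completer: Weeks 3, 9, 24 = 3.
- Non-responder completer: Weeks 3, 9, 24, 36, 48 = 5.
- Both are maxima; a subject who leaves the Treatment Period early has no Week 24 sample.

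**Step 2. Effect of sample count.** Let p be the chance that any one post-dose sample is positive, equal and independent across samples. P(at least one positive in k samples) = 1 − (1 − p)^k.

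| p | k = 3 | k = 5 |
|---|---|---|
| 0.02 | 1 − 0.98³ = 5.9% | 1 − 0.98⁵ = 9.6% |
| 0.05 | 1 − 0.95³ = 14.3% | 1 − 0.95⁵ = 22.6% |
| 0.10 | 1 − 0.90³ = 27.1% | 1 − 0.90⁵ = 41.0% |

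Independence gives a larger gap than persistent antibody would. If every subject who turns positive has done so by Week 24, the gap is 0.

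**Step 3. From enrollment type to the tabulated columns.** With relapse share w, column rate = w × (3-sample rate) + (1 − w) × (5-sample rate). Take p = 0.05 and no Day 1 positives.
- w = 40% (HZN-001) and 5% (placebo): 0.40 × 0.1426 + 0.60 × 0.2262 = 19.3%, against 0.05 × 0.1426 + 0.95 × 0.2262 = 22.2%.
- w = 10% in both: 21.8% in both, no difference.
- w = 5% (HZN-001) and 20% (placebo): 22.2% against 21.0%, the reverse direction.

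**Step 4. Effect of Day 1 positives.** Let q be the share of the HZN-001 column positive on Day 1, with q = 0 in the placebo column, and let r be the post-dose rate among Day 1 negatives.
- Third measure over all subjects = (1 − q) × r.
- Third measure over Day 1 negatives = r.
- Overall positive = q + (1 − q) × r.

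With r = 19.3% (first mix in Step 3) and q = 0.10:
- third measure, default denominator: 0.90 × 19.3% = 17.4%
- third measure, Day 1 negatives only: 19.3%
- overall positive: 10% + 17.4% = 27.4%, against 22.2% in the placebo column

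The third measure falls and overall positive rises in the same column. Overall positive in the HZN-001 column is below placebo only if q < (0.2220 − 0.1928) / (1 − 0.1928) = 3.6%. Across p = 0.02 to 0.10 and three mixes with more relapse subjects in the HZN-001 column (20% against 0%, 40% against 5%, 60% against 10%), this break-even runs from 0.8% to 10.3%.

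**Step 5. Effect of the changes.** Cutting at Week 24 gives every completer 3 post-dose samples, so both enrollment types read 14.3% at p = 0.05. Basing the third measure on Day 1 negatives removes the factor (1 − q).

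**The case against.** The strongest reply is that the plan already contains much of the answer. By-visit incidence does not accumulate. It shows Day 1 positivity and compares the lead-in columns on equal terms at Weeks 3, 9 and 24. Day 1 positives can be roughly recovered as overall positive minus the third measure (27.4% − 17.4% = 10% above). Individual results are listed, the display is descriptive with no test attached, and the third measure states exactly what it counts. All of this stands, and it keeps the point small. It does not repair the cumulative percentages as printed, and neither by-visit incidence nor subtraction shows a rise in titer.

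A reader might also infer three stronger things that the documents do not support.

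- *That ADA in the re-treated column is understated in general.* Overall positive is not restricted to post-dose samples or to Day 1 negatives, so antibody carried over from the lead-in raises that column.
- *That equal immunogenicity would look about 1.6-fold different between the columns.* The ratio 22.6/14.3 compares enrollment types under independence. In the 40%/5% mix the column ratio is 22.2/19.3 = 1.15, and in other mixes it vanishes or reverses.
- *That relapse subjects must concentrate in the HZN-001 column.* This is plausible, because relapse requires a lead-in response. But the 69% and 20% in Protocol 7.1.3.4.2 are combined CAS-and-proptosis response rates from a different study and say nothing about who relapsed or enrolled here.

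**Conclusion.** The point holds in two limited parts.

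First, the subject-level measures pool at most 3 post-dose samples for relapse completers with 5 for non-responder completers. The difference between enrollment types lies between zero (all positives by Week 24) and, under independence, figures such as 14.3% against 22.6% at p = 0.05. Its direction between lead-in columns is unknown, because the relapse mix is not given.

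Second, under the default denominator the Day-1-negative-then-positive percentage is multiplied by (1 − q) in the re-exposed column, a relative loss equal to the share positive on Day 1. This applies only if some re-exposed subjects are Day 1 positive, and only to that measure. No planned summary shows a titer rise on re-treatment.

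No primary or secondary endpoint is affected. This is an inexpensive improvement to a descriptive safety summary.

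**What to change.** In SAP 10.4:

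- (a) Report the three subject-level measures through Week 24, the visits common to both enrollment types, by lead-in treatment and by enrollment type. Report Weeks 36 and 48 separately for non-responders.
- (b) Base the Day-1-negative-then-positive percentage on subjects with a negative HZNP-TEP-302 Day 1 result, and state that denominator.
- (c) Add a treatment-boosted category for Day 1 positives, defined by a post-dose titer rise above a multiple of the Day 1 titer, with the multiple fixed before the analysis.
- (d) Repeat the measure of new positivity against HZN-001 Baseline, only where an ADA sample from before the first lead-in dose exists. The schedule lets final lead-in ADA results serve as Day 1 values, which implies lead-in ADA sampling, but a sample before the first dose is not documented.

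Items (a) to (c) use samples this study already collects, assuming that titers are recorded as values; (d) depends on lead-in data not described here. The cost is SAP wording and a few table rows. The downside is smaller cells once the columns are split by enrollment type.

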10.5. PHYSICAL EXAMINATION

A physical examination will be performed at Baseline (Day 1) and thereafter at Weeks 1, 6, 12, 18, 24 or PW during the Treatment Period and at Weeks 48 (or PW) of the Follow-Up Period. The physical examination will include assessment of presence or absence of pretibial myxedema on Day 1 and Week 24 (or PW) of the Treatment Period, and Week

48 (or PW) of the Follow-Up Period. If present, measurements of instep and calf will be taken.

A shift table will be presented providing the count of subjects with a presence or absence of pretibial myxedema at Study Baseline compared to each post-baseline visit for each side by treatment received in HZNP-TEP-301 with percentages based on subjects with a non-missing value at the Study Baseline and post-baseline visit. Further, an overall shift table will be provided capturing the worst assessment between the right and left side at Study Baseline compared to each post-baseline visit.

Similar summaries will be provided comparing to the HZN-001 Baseline.

10.6. OPTHALMIC EXAMINATION

A complete undilated ophthalmic examination will be performed as part of the physical examination. The ophthalmic exam should include best-corrected visual acuity, pupil exam, color vision assessment, Ishihara color plates (or equivalent) or related red desaturation, intraocular pressure and slit lamp exam. If significant abnormalities are noted compared with previous visits, including a loss of 2 lines or more of vision, development of pupil abnormalities including APD, rise in intraocular pressure, development of corneal infiltrates or other abnormalities not here specified but of concern to the ophthalmologist, further investigations of visual function will be conducted according to the ophthalmologist decision.

New findings reported from on-study ophthalmic examinations will not be reported as AEs if according to the investigator the abnormalities are related to TED and not related to the study drug.

For each of the assessments (pupil exam, color vision assessment, intraocular pressure, and slit lamp exam), shift tables will be presented providing the count of subjects with each type of finding (normal, abnormal - not clinically significant [NCS], or abnormal - clinically significant [CS]) at Study Baseline compared to each post-baseline visit by treatment received in HZNP-TEP-301 with percentages based on subjects with a non-missing value at the Study Baseline and post-baseline visit. In addition, a summary table will be provided for loss of 2 lines or more of vision (yes or no) including the count and percent of subjects at each post-baseline visit.

Similar summaries will be provided comparing to the HZN-001 Baseline.

10.7. VITAL SIGNS

Blood pressure and pulse measurements will be obtained with the subject's arm unconstrained by clothing or other material and while the subject is sitting up. When possible, the same arm will be used for measurements in all study visits. Assessment of vital signs, including heart rate, systolic blood pressure, diastolic blood pressure, respiratory rate, and temperature will be performed at all clinic visits. On Day 1 and

Week 3, vital signs will be measured at pre- and post-infusion. For all other visits, vital signs will be measured prior to infusion only. In addition, if immediate infusion-associated events are noted during the infusion, vital signs will be monitored every 5 minutes until stable and then every 15 minutes for 2 additional determinations. Also, vital signs will be monitored every 15 minutes from the start of the infusion through 60 minutes after infusion completion for any subsequent infusions after the previous occurrence of immediate or delayed infusion-associated events.

Weight will be measured at baseline and Week 12 and Week 24 (or PW) during the Treatment Period and Week 36 and Week 48 (or PW) during the Follow-Up Period.

Descriptive summaries of observed, change from Study Baseline values, and change from HZN-001 Baseline values will be presented for each vital sign parameter (including weight) by visit and treatment received in HZNP-TEP-301 and overall. Vital sign measurements that are monitored as a result of an infusion-associated event as described above will not be included in the descriptive summaries but will be presented in subject listings.

The following conversion factor will be used to convert any temperatures reported in degrees Fahrenheit to Celsius:

Temperature (in °C) = 5/9 (Temperature [in °F]-32).

10.8. CLINICAL LABORATORY SAFETY EVALUATIONS

With the exception of urine pregnancy tests, a central study laboratory will be used for all protocol-specified clinical laboratory parameters. [Table 3](#) provides the schedule of collection.

Table 3 Schedule of Clinical Laboratory Safety Tests, Including Thyroid Panel and Hyperglycemia Monitoring

Analysis Panel	Treatment Period											Follow-Up Period		
	BL ¹	W1	W3	W4 M1	W6	W9	W12 M3	W15	W18	W21	W24 M6	W28 M7	W36 M9	W48 M12
Chemistry (excl. glucose)	X ²		X		X	X	X		X		X		X	X
Thyroid (FT3, FT4, TSH) ³	X		X		X	X	X		X		X		X	X
Hematology	X	X	X	X	X	X	X	X	X	X	X		X	X
Glucose ⁴	X	X	X	X	X	X	X	X	X	X	X		X	X
HbA1C	X ⁵						X				X		X	X
Urinalysis	X		X		X	X	X		X		X		X	X
Urine pregnancy ⁶	X		X		X	X	X	X	X	X	X	X	X	X

BL=Baseline; FT3=free triiodothyronine; FT4=free thyroxine; HbA1C=glycated hemoglobin A1C; M=Month; SCR=Screening; TSH=thyroid stimulating hormone; W=Week.

1. If Day 1 (Baseline) of the extension study occurs on the same day as the final visit of HZNP-TEP-301, assessments do not need to be repeated, and the final assessments from the lead-in study will serve as the Baseline assessments for the extension study.
2. ALT /AST must be ≤ 3 x the ULN and serum creatinine must be < 1.5 x the ULN (according to age) at most recent clinic visit for enrollment.
3. Subjects must be euthyroid with the baseline disease under control or have mild hypo- or hyperthyroidism (defined as FT4 and FT3 levels < 50% above or below the normal limits) at the most recent clinic visit. Every effort should be made to correct the mild hypo- or hyperthyroidism promptly and to maintain the euthyroid state for the full duration of the clinical trial.
4. Non-diabetic subjects will fast at Weeks 1 and 4 only. Diabetic subjects will fast for each blood glucose evaluation. NOTE: Subjects with severe hyperglycemia that does not abate to mild or moderate intensity with anti-diabetic treatment (dose may be skipped up to 2 times prior to permanently discontinuing study drug, see Section 9.4.6.3.2 for details) will be permanently discontinued from study drug.
5. HbA1C must be < 9.0% at most recent clinic visit for enrollment. If the HbA1C is elevated and considered clinically significant at any time point after Baseline, it will be repeated approximately every 45 days until it returns to normal or baseline value.
6. Perform for female subjects of childbearing potential (including those with an onset of menopause <2 years prior to Screening of HZNP-TEP-301, non-therapy-induced amenorrhea for <12 months prior to Screening of HZNP-TEP-301, or not surgically sterile [absence of ovaries and/or uterus]).

Laboratory results collected in conventional units will be converted to International System of Units (SI) for all summaries and listings. Clinical laboratory test results (hematology, chemistry, thyroid panels, and urinalysis), their changes from Study Baseline, and their changes from HZN-001 Baseline will be summarized by visit and treatment received in HZNP-TEP-301 using descriptive statistics. If a continuous laboratory value is reported as either below or above the limits of quantification, the qualifiers will be dropped and the numeric value used in the analysis (e.g., “< 3” will be summarized as “3” and “> 200” will be summarized as “200”). For hematology, chemistry and thyroid panel, results will be categorized as low, normal, or high based on their normal ranges. For urinalysis tests, results will be classified as normal or abnormal. Results out of range will be identified as such on subject listings. Shift tables for hematology and chemistry panels using categories of low, normal, and high, comparing laboratory test results from

Study Baseline and HZN-001 Baseline to each visit will be presented overall and by treatment received in HZNP-TEP-301 with percentages based on subjects with a non-missing value at Baseline and post-baseline visit. Shift tables for urinalysis results using categories of normal and abnormal, comparing laboratory test results from Study Baseline and HZN-001 Baseline to each visit will be presented overall and by treatment received in HZNP-TEP-301 with percentages based on subjects with a non-missing value at Baseline and post-baseline visit. Additionally, a shift table for glucose by Common Terminology Criteria for Adverse Events (CTCAE) grade and visit will be presented overall and by treatment received in HZNP-TEP-301. Summaries will be provided separately for hyperglycemia and hypoglycemia.

